5.1.2 Day 1 (Study Treatment)

The following procedures will be completed during the Day 1 visit ([Table 5–1](#)).

Inclusion/exclusion criteria ([Section 4.1](#) and [Section 4.2](#), respectively) will be reviewed again to confirm the subject's eligibility to keep participating in the trial, with the Investigator verifying eligibility.

If meeting the eligibility criteria, study subjects will be randomized to study treatments and all subjects will receive EYP-1901 or sham IVT injection in the designated study eye on Day 1.

For subjects with unilateral NPDR, the affected eye will be designated as the study eye; for subjects with bilateral NPDR, the study eye will be the more severely affected eye meeting the inclusion/exclusion criteria, ie, the eye having the worse DRSS or if equal, the eye clinically judged to be the more severely affected eye as determined by the Investigator. If the eyes are symmetrically affected, the study eye will be the right eye. The fellow eye will receive treatment as needed and according to the Investigator's judgment.

Ocular procedures to be performed with data collected for both eyes (unless otherwise specified):

- ETDRS BCVA ([Appendix 1](#))
- IOP, pre- and post-injection ([Appendix 2](#))
- Ocular examination – dilated ophthalmoscopy, IOP, and slit lamp biomicroscopy ([Appendix 2](#)); check central retinal artery perfusion following study injection
- CFP
- SD-OCT assessment

Non-ocular procedures to be performed:

- Vital sign measurements ([Section 7.3](#))
- Blood sampling for PK analysis ([Section 9](#))
- Use of concomitant medications ([Section 7.5](#))
- Adverse events ([Section 7.1](#))

Throughout the study, unscheduled visit assessments may be performed as necessary at the discretion of the Investigator and following Sponsor approval. During an unscheduled visit or if posterior inflammation is present in study eye, CFP, SD-OCT, and wide-field FA of the study eye should be collected at a minimum.

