3.1.1 General Study Methods

For subjects with unilateral NPDR, the affected eye will be designated as the study eye; for subjects with bilateral NPDR, the study eye will be the more severely affected eye meeting the inclusion/exclusion criteria, ie, the eye having the worse Diabetic Retinopathy Severity Scale (DRSS) score or if equal, the eye clinically judged to be the more severely affected eye as determined by the Investigator. If the eyes are symmetrically affected, the study eye will be the right eye. The fellow eye will receive treatment as needed and according to the Investigator's judgment.

Subjects ≥18 years of age with type 1 or 2 diabetes mellitus (documented hemoglobin A1c [HbA1c] ≤12%) and an active diagnosis of moderately severe to severe NPDR (based on DRSS levels 47 or 53) in whom pan-retinal photocoagulation (PRP) and anti-VEGF injections can be safely deferred for at least 6 months as per the Investigator, and who satisfy all other protocol eligibility criteria up until dosing on Day 1, will be enrolled and receive the assigned study treatment.

Study procedures will include: ETDRS-DRSS score on 4-widefield digital stereoscopic fundus photography, best corrected visual acuity (BCVA) by ETDRS, anterior/posterior segment ocular examination, intraocular pressure (IOP), wide-field fluorescein angiography (FA), color fundus photography (CFP), ocular and non-ocular treatment-emergent adverse events (TEAEs), clinical laboratory evaluations (HbA1c, hematology, serum chemistry, coagulation, and urinalysis), bioanalytical testing for plasma levels of vorolanib and X-297, its main metabolite, heart rate and blood pressure measurements, spectral-domain – optical coherence tomography (SD-OCT),

and, at study sites where equipment is available, OCT-angiography (OCT-A). Photographs will be sent to the central reading center (CRC) for analysis.

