3.4 Duration of Study

Total study participation will be approximately 52 weeks (including the Screening period). After the initial Screening Visit, subjects may have between 5 and 30 days to be enrolled, at which point the study treatments/control will be administered on Day 1, if the eligibility criteria are still met. Subjects who require a longer period between initial screening and Day 1 will be re-screened prior to entry into the study. After Day 1 study treatment dosing, the follow-up period will be through 48 weeks (with visit windows of ± 7 days starting at Week 4). Eligible subjects who are enrolled in this study will be seen for the scheduled study visits over approximately 12 months depending on the time between Day 1 and the final study visit. Screen

failures will be recorded along with the reason(s) for not meeting the eligibility criteria. Study completion is achieved at the Week 48 visit (End of Study Visit).

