4 SELECTION AND WITHDRAWAL OF SUBJECTS

Three treatment groups of up to 20 subjects each will be enrolled to assess the efficacy and safety of 2060 µg or 3090 µg EYP-1901 intravitreal insert compared to sham IVT injection.

Subjects will be enrolled in the study only if they meet all the following eligibility criteria; continued eligibility will be assessed again at treatment randomization on Day 1. The Investigator will exercise medical and scientific judgement in deciding whether a laboratory finding, or other assessment should be reassessed within the Screening Period. Subjects that do not meet all the requirements as outlined in the eligibility criteria (screen failures), may be rescreened at the discretion of the Investigator.

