34. History or presence of bleeding disorders, including platelet disorders, hemorrhage, acquired or hereditary coagulation disorders (including deep vein thrombosis and pulmonary embolisms), acquired or hereditary vascular disorders, stroke, or transient ischemic attack in the past 2 years.

35. Excluding certain skin cancers (specifically, basal cell carcinoma and squamous cell carcinoma), any malignancy receiving treatment, or in remission less than 5 years prior to study entry.
36. History of allergy to fluorescein, not amenable to treatment.
37. Inability to obtain fundus photographs, wide-field FA, fundus autofluorescence, or SD-OCT images of sufficient quality to be analyzed and graded by the CRC.
38. Historical or active diagnosis of any medical or psychological condition that could interfere with the ability of the subject to give informed consent, or to comply with study or follow-up procedures.
39. Previous participation in any ocular or non-ocular (systemic) disease studies of investigational drugs within 30 days prior to the Screening Visit (excluding vitamins and minerals).
40. Use of anti-mitotic or anti-metabolite therapy within 30 days or 5 elimination half-lives of the Screening Visit, whichever is longer.
41. Intolerance, contraindication, or hypersensitivity to topical anesthetics, dyes, povidone iodine, mydriatic medications, or any of the ingredients of the EYP-1901 insert.
42. Requirement for continuous use of any protocol-prohibited medications or treatments.
43. Pregnant or nursing females; females of childbearing potential who are unwilling to use an acceptable method of contraception during the study as outlined in this protocol.

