4.3 Pregnancy and Contraception

Women of childbearing potential must be practicing and willing to continue using a highly effective method of birth control during the course of the study, such as: oral contraceptive pill (eg, Ortho Tri-Cyclen[®]); injection (eg, Depo Provera[®]); implant (eg, Norplant[®]); patch (eg, Ortho Evra Patch[®]); vaginal ring (eg, NuvaRing[®]); intrauterine coil (eg, Mirena[®] coil); intrauterine device (IUD) with or without hormones; a barrier method (eg, latex condom, diaphragm, or cap) used **with an additional form of contraception** (ie, **two methods** [eg, sponge, spermicide, hormonal contraceptive pill, or injection]); or complete abstinence. A female is considered to be of childbearing potential UNLESS she is post-menopausal (no menses for two consecutive years) or without a uterus and/or both ovaries.

Before enrolling a woman of childbearing potential, Investigators must review with the subject the following:

- Pregnancy prevention information
- Risks to unborn child(ren)
- Risks if currently nursing
- Any drug interactions with hormonal contraceptives
- Contraceptives in current use (or if complete abstinence is being followed)
- Guidelines for the follow-up of a reported pregnancy

For subjects who become pregnant during the study positive urine pregnancy results will be confirmed by a serum pregnancy test. Based on the anti-VEGF mechanism of action of EYP-1901, the study treatments may pose a risk to human embryofetal development. Subjects should continue participation in the study at the discretion of the Investigator and only if the potential benefit justifies the potential risk to the fetus. Subjects should be instructed to notify the Investigator if it is determined after completion of the study that they became pregnant while participating in the study. However, it is the Investigator's responsibility to pursue the follow-up. Whenever possible, a pregnancy should be followed to term, any premature terminations of pregnancy should be reported, and the status of the mother and the child should be reported to the Medical Monitor after delivery.

Subjects who are not of childbearing potential meeting one or both of the following criteria will not be required to be tested for pregnancy or use contraception:

- Amenorrheic for >2 years without a hysterectomy and bilateral oophorectomy and a FSH value in the postmenopausal range upon pre-trial (screening) evaluation.

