5.1.1 Day -30 to Day -5 (Screening Visit)

The following procedures must be completed during the initial Screening Visit ([Table 5–1](#)):

Informed Consent: Properly executed informed consent (written and verbal) is to be obtained prior to completion of any trial related procedures. A subject may take as long as needed to review the informed consent form (ICF) and consider trial participation; they may take the document with them and return at a later date (provided the study is still open for enrollment). The subject must review, sign and date the document, and receive a copy.

Inclusion/Exclusion Criteria: Inclusion/exclusion criteria ([Section 4.1](#) and [Section 4.2](#), respectively) will be reviewed to determine the subject's eligibility to participate in the trial with the Investigator verifying enrollment eligibility.

Demography, Medical History, and Medication History: Demography, complete medical history, and recent (previous 30 days) medications ([Section 6.6.1](#)) are to be recorded. Current contact lens use or ocular trauma in the study eye must be documented.

Ocular procedures to be performed with data collected for both eyes:

- ETDRS BCVA ([Appendix 1](#))
- Ocular examination – dilated ophthalmoscopy, IOP, and slit lamp biomicroscopy ([Appendix 2](#))
- CFP
- Wide-field FA
- SD-OCT assessment
- SD-OCTA assessment (at pre-specified study sites where equipment is available)

Non-ocular procedures to be performed:

- Vital sign measurements ([Section 7.3](#))
- ECG ([Section 7.4](#))
- Collect blood and urine samples for clinical laboratory evaluations ([Section 7.2](#))
- Documented HbA1c $\leq 12\%$ for Inclusion Criterion #1 (confirmed by laboratory evaluation at the Screening Visit or by a documented laboratory report dated within 60 days prior to the Screening Visit).
- Urine pregnancy test (females of childbearing potential only)
- Use of concomitant medications ([Section 7.5](#))
- Adverse events, which will be collected from the time the ICF is signed ([Section 7.1](#))

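### The Day 1 re-check of the pregnancy exclusion rests on a urine test taken 5 to 30 days earlier, and no scheduled test is current at dosing

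*Protocol*

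**What the plan says.** **Eligibility must hold at dosing.** Protocol 3.1.1 enrols and treats subjects "who satisfy all other protocol eligibility criteria up until dosing on Day 1". Protocol 3.4 makes Day 1 treatment conditional on the criteria still being met. Protocol 4 states that "continued eligibility will be assessed again at treatment randomization on Day 1". Protocol 5.1.2 repeats the review on Day 1 to confirm "eligibility to keep participating in the trial, with the Investigator verifying eligibility".

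**Pregnancy is one of those criteria.** Exclusion 43 in Protocol 4.2 begins "Pregnant or nursing females". Protocol 4.3 adds that, given the anti-VEGF mechanism, "the study treatments may pose a risk to human embryofetal development".

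**The test is scheduled at two points.** Protocol 5.1.1 lists it at Screening: "Urine pregnancy test (females of childbearing potential only". Protocol 5.1.7 lists it again at Week 48 or early termination. In Table 5-1 and SAP Table 1 the urine-test row is blank at Day 1 and at Weeks 4, 12, 24 and 36. The Day 1 list in 5.1.2 has no pregnancy test and no clinical laboratory collection. A serum test is used only to confirm a positive urine result.

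**The interval is stated.** Under Protocol 3.4, after Screening "subjects may have between 5 and 30 days to be enrolled".

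**The concern.** The plan asks the Investigator to verify on Day 1 that no exclusion applies, but schedules nothing that measures pregnancy at that visit. Pregnancy status can change between Screening and Day 1, and a very early pregnancy can be missed at Screening. A subject in either situation could be randomized as eligible with the plan followed to the letter.

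This matters more here than for a drug given in repeated doses. Protocol 6.5 describes EYP-1901 as single-delivery with no dose modification, and Protocol 6.1 gives a release period of at least 9 months. An error at the Day 1 check cannot be corrected by changing a later dose.

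Protocol 4.3 also describes serum confirmation of positive urine results in subjects who become pregnant during the study. For a completer, no urine test is scheduled after Screening until the final visit.

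**Working it through.** **Inputs**
- Screening on Day -30 to Day -5 (Protocol 5.1.1, Table 5-1, SAP Table 1).
- No Study Day 0 (SAP 8.2).
- Week 48 target = Study Day 336 (SAP 8.4, Table 2); visit window ±7 days (Protocol Table 5-1).
- 1:1:1 allocation of about 60 subjects, two arms active (Protocol 3.1, 11.1).
- Release of at least 9 months (Protocol 6.1).

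**Step 1. Reproduce the stated interval.** With no Day 0, days from Day -k to Day 1 = 1 + k - 1 = k.
- Day -5 to Day 1: 5 days.
- Day -30 to Day 1: 30 days.

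This matches the 5 to 30 days in Protocol 3.4. It is the age, at dosing, of the only scheduled pregnancy result.

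**Step 2. Gap between scheduled tests for a completer.** Days from Day -k to Day 336 = 336 + k - 1.
- k = 5: 340 days. k = 30: 365 days.
- With ±7 days at Week 48: 340 - 7 = 333 to 365 + 7 = 372 days.

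**Step 3. Compare with the release period.** Nine months is about 9/12 × 365 = 274 days. The earliest in-window Week 48 visit is Day 336 - 7 = 329. For a completer, no scheduled test falls in the first nine months after dosing.

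**Step 4. Who receives an insert.** Two of three arms: 2/3 × 60 = 40 subjects. The other 20 receive sham.

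**Step 5. How many women this could concern.** The documents do not give the number of women of childbearing potential. Assuming 5% to 20% of 60, that is 3 to 12 women, of whom 2/3, or 2 to 8, would receive an insert. This counts women dosed on a result of that age, not pregnancies, and the conclusion does not depend on it.

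**Step 6. Is the blank Day 1 cell a reading error?** No. Protocol Table 5-1, the lists in 5.1.1 to 5.1.7 and SAP Table 1 all agree. SAP 8.4 likewise refers to urine pregnancy data only at baseline and Week 48/end of treatment.

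The SAP visit-window tables (Tables 2 to 5) still give Screening as Day -21 to -5, unlike SAP Table 1 and the protocol. On that window the result would be 5 to 21 days old, which leaves the point unchanged.

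**The case against.** The best defence is that 5.1.2 asks for criteria to be reviewed again, not for every measurement to be repeated. HbA1c and wide-field angiography also have no Day 1 measurement, although entry criteria depend on them. Women must already be using highly effective contraception, and prevention and fetal risk are discussed before enrolment (4.3). Pregnancies are reportable within 24 hours of awareness (7.1.7.1). Subjects are seen at Weeks 4, 12, 24 and 36, and unscheduled assessments are possible with Sponsor approval (5.1.2).

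Much of this stands, and it rules out three stronger readings that a reader might infer:
- *That the Day 1 check has no result behind it, or is never made.* A Screening result exists, and the Investigator can use it with history.
- *That the passages contradict one another.* The schedules agree throughout. The 4.3 wording on in-study positives is not empty, because Week 48 and early termination are in-study visits with a urine test. The fault is a requirement without a current measurement to support it.
- *That a pregnancy would come to light only at Week 48.* Week 48 is the next scheduled test, not the only route to detection. A pregnancy already present on Day 1 would ordinarily have ended before then, and the visits and reporting rules offer other routes.

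What the defence does not answer is the interval itself. History and contraception lower the probability of pregnancy but do not measure it. For HbA1c the protocol expressly accepts a report dated up to 60 days before Screening; it makes no such statement about relying on an older pregnancy result. An unscheduled test is discretionary and does not form part of the Day 1 verification as written.

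**Conclusion.** The concern holds as a patient-safety gap. Exclusion 43 must be met and verified on Day 1, but the only scheduled evidence is a urine result 5 to 30 days old. With history and the contraception requirement, that result cannot exclude a pregnancy that began after Screening or was undetectable then. A completer has no further scheduled test until Week 48, 340 to 365 days after Screening at target. About two thirds of subjects receive the single-delivery, sustained-release insert; the sham third does not.

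The schedule facts are certain. The number of women affected is unknown, and the 3 to 12 above is an assumption. The Laboratory Manual is not among the documents, but nothing available schedules a pre-dose repeat. No efficacy endpoint, estimate or analysis is affected.

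**What to change.** Reconcile the Day 1 eligibility re-check (Protocol 4 and 5.1.2), exclusion 43 and the in-study wording of 4.3 with the pregnancy-test row in Table 5-1 and SAP Table 1. The aim is that the Day 1 verification of exclusion 43 is supported by a measurement current at dosing, and that the text says which result the Investigator verifies against. The sponsor decides the timing of testing and the handling of any positive result.

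The cost is a small protocol and SAP amendment, with the IRB/EC approval that Protocol 13.1 requires. If the sponsor chooses to add a test, it is one urine test per woman of childbearing potential at a visit that already takes place.

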5.1.3 Week 4 (± 7 days)

The following procedures will be completed during the Week 4 visit ([Table 5–1](#)).

Ocular procedures to be performed with data collected for both eyes (unless otherwise specified):

- ETDRS BCVA ([Appendix 1](#))
- Ocular examination – dilated ophthalmoscopy, IOP, and slit lamp biomicroscopy ([Appendix 2](#))
- CFP
- SD-OCT assessment

Non-ocular procedures to be performed:

- Vital sign measurements ([Section 7.3](#))
- Use of concomitant medications ([Section 7.5](#))
- Adverse events ([Section 7.1](#))

5.1.4 Week 12 (± 7 days)

The following procedures will be completed during the Week 12 visit ([Table 5–1](#)).

Ocular procedures to be performed with data collected for both eyes (unless otherwise specified):

- ETDRS BCVA ([Appendix 1](#))
- Ocular examination – dilated ophthalmoscopy, IOP, and slit lamp biomicroscopy ([Appendix 2](#))
- CFP
- SD-OCT assessment

Non-ocular procedures to be performed:

- Vital sign measurements ([Section 7.3](#))
- Collect blood and urine samples for clinical laboratory evaluations (including HbA1c) ([Section 7.2](#))
- Blood sampling for PK analysis ([Section 9](#))
- Use of concomitant medications ([Section 7.5](#))
- Adverse events ([Section 7.1](#))

5.1.5 Week 24 (± 7 days)

The following procedures will be completed during the Week 24 visit ([Table 5–1](#)).

Ocular procedures to be performed with data collected for both eyes (unless otherwise specified):

- ETDRS BCVA ([Appendix 1](#))
- Ocular examination – dilated ophthalmoscopy, IOP, and slit lamp biomicroscopy ([Appendix 2](#))
- CFP
- Wide-field FA
- SD-OCT assessment
- SD-OCTA assessment (at pre-specified study sites where equipment is available)

Non-ocular procedures to be performed:

- Vital sign measurements ([Section 7.3](#))
- Collect blood and urine samples for clinical laboratory evaluations (including HbA1c) ([Section 7.2](#))
- Blood sampling for PK analysis ([Section 9](#))
- Use of concomitant medications ([Section 7.5](#))
- Adverse events ([Section 7.1](#))

5.1.6 Week 36 (±7 days)

The following procedures will be completed during the Week 36 visit ([Table 5-1](#)).

Ocular procedures to be performed with data collected for both eyes (unless otherwise specified):

- ETDRS BCVA ([Appendix 1](#))
- Ocular examination – dilated ophthalmoscopy, IOP, and slit lamp biomicroscopy ([Appendix 2](#))
- CFP
- Wide-field FA
- SD-OCT assessment

Non-ocular procedures to be performed:

- Vital sign measurements ([Section 7.3](#))
- Collect blood and urine samples for clinical laboratory evaluations (including HbA1c) ([Section 7.2](#))
- Blood sampling for PK analysis ([Section 9](#))
- Use of concomitant medications ([Section 7.5](#))
- Adverse events ([Section 7.1](#))

5.1.7 Week 48 (±7 days, End of Study) and Early Termination Visit

Subjects who terminate the study prior to the Week 48 visit should undergo all procedures noted for the Early Termination Visit in [Table 5-1](#).

The following procedures will be completed during the Week 48 or ET visits ([Table 5-1](#)).

Ocular procedures to be performed with data collected for both eyes (unless otherwise specified):

- ETDRS BCVA ([Appendix 1](#))
- Ocular examination – dilated ophthalmoscopy, IOP, and slit lamp biomicroscopy ([Appendix 2](#))
- CFP
- Wide-field FA

- SD-OCT assessment
- SD-OCTA assessment (at pre-specified study sites where equipment is available)

Non-ocular procedures to be performed:

- Vital sign measurements ([Section 7.3](#))
- ECG ([Section 7.4](#))
- Collect blood and urine samples for clinical laboratory evaluations (including HbA1c) ([Section 7.2](#))
- Urine pregnancy test (females of childbearing potential only)
- Blood sampling for PK analysis ([Section 9](#))
- Use of concomitant medications ([Section 7.5](#))
- Adverse events ([Section 7.1](#))

5.2 Appropriateness of Measurements

The efficacy and safety assessments to be utilized in this study (eg, ETDRS-DRSS, BCVA by ETDRS, slit lamp biomicroscopy, dilated ophthalmoscopy, IOP measurements, wide-field FA, CFP, SD-OCT, SD-OCTA [where equipment is available], collection of ocular and non-ocular AEs, clinical laboratory evaluations, vital signs, ECGs, use of concomitant medications) are standard measures in studies evaluating intravitreal investigational products like EYP-1901.

6 STUDY INTERVENTIONS

6.1 Study Intervention Identification and Description

EYP-1901 intravitreal insert is a bioerodible, sterile, sustained-release drug delivery system that is designed to release microgram levels of vorolanib into the ocular vitreous chamber for the treatment of NPDR. The intravitreal insert formulation design is based on the Durasert® technology that allows EYP-1901 to exhibit the following characteristics:

- Bioerodible properties
- Sustained-release kinetics
- Prolonged duration of release (not less than 9 months)
- High drug loading
- Administration in an office setting through an intravitreal needle injection

